7.3 OTHER EFFICACY ANALYSES

Additional secondary objective is to explore the pharmacodynamic effects of COR-001 compared to placebo by evaluating changes in

- Change in hemoglobin from screening to peak hemoglobin (defined as per subject absolute maximal hemoglobin in g/dL)
- ERI and Hemoglobin from baseline (weekly mean during the Screening Period for ERI and mean of Full Screening and Day 1 for Hemoglobin) through Week 4, 12 and 24
- ERI and Hemoglobin from baseline (weekly mean during the Screening Period for ERI and mean of Full Screening and Day 1 for Hemoglobin) through Week 4, 12 and 24 stratified by baseline ERI tertiles
- ESA and parenteral iron dose requirements from baseline (weekly mean during the Full Screening Period) to Evaluation Period (Weeks 8 – 12) and through Week 24.

- Systemic iron stores (serum ferritin, hepatic and splenic iron content, and supplemental iron dose requirements) over time
 - Markers of malnutrition-inflammation (pre-albumin and albumin) over time
 - LV mass index from Screening to Week 12
 - Pre-dialysis, post-dialysis, and delta-serum Troponin and NT-proBNP (defined as the difference between the pre- and post-dialysis troponin) from baseline (mean of Screening) to Weeks 10 – 11.
 - Handgrip strength from baseline (during screening) to Week 12
- FACIT fatigue score from baseline (during screening) to Week 12

For the above efficacy variables, the observed values and changes from baseline will be summarized by treatment group using descriptive statistics for Pharmacodynamic analysis population.

Specifically, the weekly mean of ERI will be calculated and presented individually for each ESA based on the formula in [Section 1.2.3.2](#).

The mean of left and right handgrip strengths will be used for analysis no matter which hand is dominant.

The FACIT-F (Version 4) is a compilation of general questions divided into five primary domains: Physical Well-Being, Social/Family Well-Being, Emotional Well-Being, Functional Well-Being and Additional Concerns. The data in Additional Concern domain will be listed separately and considered the primary analysis for the FACIT-F. The total fatigue score will be calculated as a summation of the scores in the five primary domains. The observed value and change from baseline in total fatigue score will be summarized by treatment.

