3.5.4 Rationale for the Dose Regimens

The main goal of COR-001 dosing in the planned Phase 1/2 hemodialysis patient study is to attain and maintain serum COR-001 concentrations sufficient for $\geq 90\%$ IL-6 binding over the 3-month Treatment Period, with a secondary goal of reducing hsCRP to below 5 mg/L while keeping the highest planned dose more than 20-fold below the no adverse effect level (NOAEL) observed in primates.

Effects on IL-6 and hsCRP

Pharmacokinetic and PD models were created based on data from the Phase 1 trial in RA patients (Study D4430C00001) and used to simulate dosing regimens that achieve the above goals (Section 3.5.4). Based on these models, lower doses were needed to maintain serum COR-001 concentrations above the target value (i.e., that value required to achieve $> 90\%$ IL-6 binding) compared to those needed to normalize hsCRP (defined as $\text{hsCRP} < 5\text{mg/L}$) in a hypothetical hemodialysis population whose baseline hsCRP is at median and serum IL-6 level is above the median. hsCRP normalization in at least 1/3 patients is predicted for cumulative COR-001 dose of ≥ 12 mg, and is not predicted for all patients until cumulative doses of 60 mg or greater are achieved. The COR-001 dose regimens planned are itemized below. Lower doses (including previously studied doses) may be substituted for the planned doses in the table below based on accruing data. In addition, PK and PD results will be reviewed to assess the appropriateness of the next planned dose and to guide revision of the next dose to be evaluated, if necessary.

Dose Cohort	Dose Regimen	Number of Doses	Total Cumulative Dose
1	2 mg every 14 days	6	12 mg
2	6 mg every 14 days	6	36 mg
3	20 mg every 14 days	6	120 mg
4	60 mg every 14 days	6	360 mg

The planned doses all provide plasma IL-6 binding in excess of 90% for the duration of the study, while hsCRP normalization is expected to be attained in 1/3 of patients at the lowest dose, and in 3/3 patients at the highest dose. Full suppression of hsCRP is not believed to be required for beneficial effect on hematologic or iron parameters given the linear correlation between CRP and the degree of erythropoietic inefficiency (Bárány 1997).

As of Amendment 3, the actual doses (all given every 14 days) were 2 mg (Cohorts 1 and 4); 6 mg (Cohorts 2 and 3); 20 mg (Cohort 5).

Safety Margins

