10.2 INTERIM ANALYSIS

A single interim analysis will be conducted for the purpose of guiding future COR-001 clinical program activities. There are no stopping rules associated with the interim analysis and therefore no statistical adjustment for multiplicity will be made. The interim analysis will be conducted, at earliest, once all cohorts below that which exceed the MTD, excluding any expansion cohorts, have completed the study through Week 4 (or final visit, if prematurely discontinued).

The following endpoints will be assessed in the interim analysis:

- PD parameters: hsCRP, SAA, free and/or total serum IL-6, as well as, hemoglobin, TSAT, CHr, pre-albumin, and albumin
- Change in hemoglobin from screening to peak hemoglobin (defined as per subject absolute maximal hemoglobin in g/dL)
- Change from baseline (mean of Full Screening and Day 1 values) in Hemoglobin to Weeks 10-12, excluding hemoglobin values following a change in the total weekly ESA dose. A change is defined as the first time when the ESA weekly dose goes up by >25% or down by >25% relative to the previous week's dose.
- ERI
- Hemoglobin and ERI stratified by baseline ERI (<median or >=median)
- Cardiac biomarkers: Pro-NT-BNP and troponin
- MRI outcome: LVMI, LVESVI, LVEDVI, and LVEF
- Handgrip strength
- FACIT fatigue score

The summary approach for these listed endpoints will be the same as described in the SAP and will follow the specifications below for presentation in order to mask the treatment-level data:

- By masked treatment group (e.g. Treatment A, Treatment B, and etc.). Subjects receiving placebo from all cohorts will be combined as one of the treatment groups
 - Both PD analysis population and Per-Protocol analysis population will be performed on masked data
- Pooled treatment vs pooled placebo
- Pooled responder analysis defined as change from baseline in PD parameter for all patients (regardless of active vs placebo assignment) who achieve a $\geq 50\%$ reduction in hsCRP

To avoid identification of individual patients, the number of subjects, minimum, maximum values, and raw numbers for the percentages (i.e. numerator and denominator) will not be presented. Only the means, standard deviations, and percentages will be presented. The sponsor personnel will only receive the masked treatment group-level information and have no access to actual treatment-level information nor subject-level treatment information.

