11. DATABASE LOCK

The database will be locked sequentially to enable program planning.

- Database Lock 1 will occur after the last patient in Cohort 6 completes the Week 12 visit or early terminates prior to Week 12. All visit-specific case-report forms for all completed visits, including unscheduled visits, occurring prior to the database cutoff date will be frozen for patients in all cohorts. Because patients in Cohort 1-4 will already have completed the study, the vast majority of data will be locked at this time. Handling on non-visit specific CRFs is described below. Because the primary and secondary pharmacodynamic endpoints are based on time points through Week 12; therefore, these data will be locked with Database Lock 1 and be unaffected by subsequent database locks.
- Database Lock 2 will occur after the last patient in Cohort 6 completes the Week 24 visit or early terminates prior to Week 24. All visit-specific case-report forms for all completed visits not already locked during Database Lock 1, including unscheduled visits, occurring prior to the database cutoff date will be locked for patients in all cohorts. Handling on non-visit specific CRFs is described below.
- Database Lock 3 will occur after the last patient in Cohort 6 completes the Week 35 visit or early terminates prior to Week 35. All visit-specific case-report forms for all completed visits not already locked during Database Locks 1 and 2, including unscheduled visits, will be locked for patients in all cohorts. Adverse events, concomitant medications, and other log CRF page and end of study CRF will be handled as described below.

Database Locking Rules for Visit Non-Specific CRFs

- Adverse events, Infection Details, and Infusion-Related Reaction CRFs will be locked at Database Locks 1 and 2 if either of the below apply.
 - The AE or corresponding SAE of infection or infusion-related reaction has an end date. If the event is an SAE, the SAE case must also have been closed.
 - The patient completed the study, died, or was withdrawn from the study.

All remaining events will be locked at the time of Database Lock 3.

- Concomitant Medications will be locked at Database Locks 1 and 2 if any of the below apply:
 - The concomitant medication indication is an AE and there is an end date for the corresponding AE or the patient died or the patient was withdrawn from the study. In case of SAE, SAE case must also be closed.

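### Peak hemoglobin has no visit window, so at the interim analysis dose groups can be compared on maxima taken over unequal follow-up

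*SAP*

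**What the plan says.** SAP 7.3 lists among the other efficacy analyses "Change in hemoglobin from screening to peak hemoglobin (defined as per subject absolute maximal hemoglobin in g/dL". SAP 10.2 repeats the wording for the interim. Neither gives a window. The other hemoglobin endpoints in SAP 7.2 and 7.3 do name visits: Week 4, Weeks 10-12, and through Weeks 4, 12 and 24.

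The only general bound is the observational period in SAP 2.3, from consent to study completion. Protocol 4.6 puts primary completion at Week 24. That bound sets no common endpoint at an early data cut and does not exclude pre-dose values. SAP 2.3 keeps unscheduled visits out of by-visit summaries, but a per-subject maximum is not a by-visit summary, so their handling is open.

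On timing, the interim may run once the qualifying cohorts "have completed the study through Week 4 (or final visit, if prematurely discontinued". It reports "By masked treatment group (e.g. Treatment A, Treatment B, and etc", with placebo combined, and also pooled active against pooled placebo. In the interim output "the number of subjects, minimum, maximum values, and raw numbers for the percentages (i.e. numerator and denominator) will not be presented".

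SAP 11 states: "Database Lock 1 will occur after the last patient in Cohort 6 completes the Week 12 visit or early terminates prior to Week 12". It adds: "Because patients in Cohort 1-4 will already have completed the study, the vast majority of data will be locked at this time". Protocol 3.5.4 records: "As of Amendment 3, the actual doses (all given every 14 days) were 2 mg (Cohorts 1 and 4); 6 mg (Cohorts 2 and 3);" and 20 mg in Cohort 5. The Cohort 6 dose is not stated.

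**The concern.** The expected maximum of repeated measurements grows with their number, even when nothing changes. In a sequential design, cohort determines both dose and length of follow-up at any early data cut. An unwindowed maximum therefore carries a difference between dose groups that comes only from when they were enrolled. It runs against the most recently enrolled group.

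The interim exists to guide the later program. A peak-hemoglobin comparison in which one group looks worse through shorter observation could mislead that planning. Because subject numbers, minima and maxima are withheld, the table itself would give the reader little chance of noticing.

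**Working it through.** The plan gives no sample size, power or expected value for peak hemoglobin, so there is no figure of its own to reproduce.

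**Number of values.** Appendix A of the protocol schedules hemoglobin in Lab Panel 5. Post-dose draws:

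- Days 8, 15, 22: 3 values by the Week 4 visit
- plus Day 29: 4 values (SAP 7.1 uses Day 29 as Week 4 for hsCRP)
- plus Days 36, 43, 50, 57, 64, 71, 78: 11 values by Week 12
- plus Days 92, 106, 120, 134, 162: 16 values by Week 24, with none at Week 35

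**Expected maximum with no drug effect.** Assumptions: hemoglobin is normal and stationary, measured on the scheduled days, with correlation ρ per week between draws, so corr = ρ^(days apart / 7). The documents give neither ρ nor the within-patient SD. I took ρ from 0 to 0.9 and simulated 400,000 patients per setting. The baseline has the same expectation in every group, so it cancels from the differences. Results in within-patient SD units:

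| ρ per week | 3 values (Day 22) | 4 values (Day 29) | 11 values (Week 12) | 16 values (Week 24) |
|---|---|---|---|---|
| 0 | 0.846 | 1.028 | 1.586 | 1.765 |
| 0.5 | 0.644 | 0.820 | 1.419 | 1.663 |
| 0.8 | 0.421 | 0.553 | 1.080 | 1.395 |
| 0.9 | 0.299 | 0.397 | 0.823 | 1.135 |

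**False difference = E[max, newest group] − E[max, comparison group].**

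- *Interim, worst case (newest at Week 4, others at Week 24).* Smallest: 1.028 − 1.765 = −0.74 (ρ = 0, Day 29). Largest: 0.644 − 1.663 = −1.02 (ρ = 0.5, Day 22). At an assumed SD of 0.5 to 0.7 g/dL this is 0.74 × 0.5 = 0.37 to 1.02 × 0.7 = 0.71 g/dL.
- *Interim, compared cohorts only at Week 12 and newest at Day 29.* From 0.397 − 0.823 = −0.43 (ρ = 0.9) to 0.820 − 1.419 = −0.60 (ρ = 0.5), or 0.21 to 0.42 g/dL at the same SDs.
- *Lock 1, upper bound (11 against 16 values).* From 1.586 − 1.765 = −0.18 (ρ = 0) to 1.080 − 1.395 = −0.32 (ρ = 0.8), or 0.09 to 0.22 g/dL.

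**Against pooled placebo.** Take five cohorts, four at Week 24 and one at Week 4, each 8:2. The placebo mean is (8·m24 + 2·m4)/10.

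- Newest dose: m4 − placebo = 0.8 × (m4 − m24), which is −0.59 to −0.82 SD.
- Older doses: m24 − placebo = 0.2 × (m24 − m4), which is +0.15 to +0.20 SD.
- Pooled active: (32·m24 + 8·m4)/40 − (8·m24 + 2·m4)/10 = 0.

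**After the fix.** With one window, every group has the same scheduled count (3 or 4, or 11). The false difference is then 0 under no drug effect, apart from missed visits.

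**The case against.** The strongest reply is that the harm is limited.

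- *Week 4 is only the earliest cut.* The interim list also contains hemoglobin at Weeks 10-12 and MRI outcomes, whose follow-up scan is at Week 12, which suggests a later cut. With the newest cohort at Week 12 the gap is no more than the 0.18 to 0.32 SD computed for Lock 1. This stands as a limit on size, but the rule still permits the Week 4 cut.
- *Interim groups are masked.* A reader who cannot identify the doses cannot read a dose response from them. This also stands. Masking hides the labels, however, and leaves the bias of each masked group against pooled placebo in place.
- *Pooled active versus pooled placebo is unaffected.* Correct, because allocation is 8:2 in every cohort.
- *Other endpoints carry the hemoglobin question.* SAP 7.2 has windowed hemoglobin endpoints with ANCOVA by dose. Peak hemoglobin is one descriptive line, so no formal error rate is involved.

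A reader might infer three stronger points that the documents do not support. First, that the 20 mg cohort is shown to be disadvantaged at Lock 1. The SAP says only "Because patients in Cohort 1-4 will already have completed the study". Cohort 5 precedes Cohort 6 and may already have all 16 values, the Cohort 6 dose is not given, and the SAP does not say that peak hemoglobin is reported at that lock. Second, that peaks after Week 12 reflect ESA titration and not study drug. Appendix C of the protocol allows titration from Week 5, and Protocol 4.3 describes a long pharmacodynamic effect. Third, that the 1 g/dL rise in SAP Table 2 is a yardstick for these differences. That is a threshold for individual patients, not for group means.

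**Conclusion.** The concern holds in a limited form. As written, the rule can compare maxima of 3 or 4 values with maxima of up to 16. With no drug effect it then understates the newest group by about 0.74 to 1.02 within-patient SD at the earliest permitted interim, or about 0.43 to 0.60 SD if the compared cohorts have reached only Week 12 when the newest is at Day 29. At Lock 1 the understatement is at most about 0.18 to 0.32 SD, for whichever group is still at Week 12 and only if the endpoint is reported then. It is zero once all patients reach Week 24.

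The direction follows from the visit counts under a stationary model. The SD-unit figures also assume normality and ρ from 0 to 0.9, and the g/dL figures an SD of 0.5 to 0.7. The documents do not give the actual interim date or confirm that 20 mg was included. The change is worth making because the definition builds in a bias and costs little to correct.

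**What to change.** In SAP 7.3 and 10.2, define peak hemoglobin as the maximum of scheduled post-dose values within one window that all included cohorts have completed at that data cut. Examples are through Week 4 for an interim at its earliest cut, and through Week 12 for Lock 1 and the final report. State that unscheduled values are excluded.

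The cost is one SAP sentence and a date filter in the program. The downside is that peaks after the window appear only in the over-time summaries. Patients who miss visits or leave early will still contribute fewer values.

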Section 4.4	Addition of dose-escalation rule	NA	In addition, if 1 of 8 COR-001-treated patient in a cohort experiences a Grade 4 or 5 DLT, the dose will not be escalated.	Avoids dose-escalation if a single Grade 4 or 5 DLT was observed
Section 5.1.3	Stool occult blood test revision	Stool cards	Stool tests Stool samples	Central lab stool testing does not use cards
Section 5.1.4	Revision of weekly study activity descriptors	Study activities described based on weekly dosing	Study activities described based on every two week dosing	Updated study activity timing to align with every two week dosing and added additional PK/PD time points
Section 6.1.1	Update of drug reconstitution and administration instructions, tables and schematics	NA	Revised text, tables and schematics	Provide updated instructions for COR-001 and associated administration materials handling based on revised dosing schedule
Schedule of Events	Revised PK and PD sampling	PK/PD schedule appropriate to weekly dosing	PK/PD schedule appropriate to every other week dosing	Align PK/PD assessments with revised dosing schedule and add additional PK/PD time points. Assess potential for dialysis clearance of COR-001.
Schedule of Events	ADA sampling during Treatment Period	Weekly	Every 2 weeks prior to dosing	ADA sampling adjusted to match revised dosing schedule

Schedule of Events	Addition of footnote 14	NA	Visit window may be extended to +4 days only in instances when the study drug was missed on the targeted visit day and also could not be given during the dialysis visit after the missed dose.	Proportional increase in visit window for drug dosing (i.e. from 2-day window for q7day dosing to 4-day window for q14d dosing)
Synopsis Section 4.1	Correction of ERI formula	Multiplier of 300 in the denominator; result expressed in mcg/kg per dL	Multiplier of 300 in the numerator; result expressed in units/kg per dL	Corrected error in conversion for darbepoetin and methoxy polyethylene glycol-epoetin beta to epoetin equivalents for calculation of ERI
Schedule of Events	Revised timing of cardiac markers pro-NT-BNP and troponin at terminus of treatment period	Weeks 10, 11, 12	Week 11 Day 71, Week 11 Day 75, Week 12	Maintain timing of these markers with the last 3 visits of the Treatment Period (Day 71, Day 75, and Week 12)
Table of Contents	Updated	NA	NA	Updated to reflect changes listed above

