- Description of changes in pre-dialysis, post-dialysis, and delta-serum Troponin and NT-proBNP (defined as the difference between the pre- and post-dialysis troponin) from baseline (mean of Screening) to Weeks 11 – 12
- Handgrip over time
- FACIT fatigue score over time

For the above efficacy variables, the observed values and changes from baseline will be summarized by treatment group using descriptive statistics using mITT and PP populations.

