Study Week(s)	7	8	9	10	11		12/ET-1
Visit Window	±2 ¹⁴	±2	±2 ¹⁴	±2	±2 ¹⁴		±2
Study Day(s)	43	50	57	64	71	75	78
ESA and iron dosing per Appendix C							
Study Drug Administration [1]	X		X		X		
Lab Panel 1 [CHEM]							X [a]
Albumin				X			
Lab Panel 2 [LIP], Lp(a),							X [a]
Lab Panel 3 [INFL1]	X [a]		X [a]	X [a]	X [a]		X [a]
hsCRP	X [a]	X [d]	X [a]	X [a]	X [a,b,c]	X [a,d]	X [a]
Pre-Albumin	X [a]	X [d]	X [a]		X [a,b,c]	X [a,d]	X [a]
Lab Panel 4 [SPRBC]	X [a]	X [a]	X [a]	X [a]	X [a]		X [a]
Lab Panel 5 [HEME]	X [a]	X [a]	X [a]	X [a]	X [a]		X [a]
Lab Panel 6 [IRON]	X [a]	X [a]	X [a]	X [a]	X [a]		X [a]
Lab Panel 7 [PK]	X [a]	X [d]	X [a]		X [a,b,c]	X [a,d]	
Lab Panel 8 [CARD]					X [a,d]	X [a,d]	X [a,d]
Lab Panel 10 [ADA]	X [a]		X [a]		X [a]		
Lab Panel 11 [INFL2]	X [a]	X [d]	X [a]		X [a,b,c]	X [a,d]	X [a]
Lab Panel 12 [BIO]							X [a]
Serum pregnancy [2]							X [a]
Local Lab INR [3]	X [a]	X [a]	X [a]	X [a]	X [a]		X [a]
12-lead ECG pre-dialysis							X
FACIT-F [13]							X
Limited Physical Examination [5]							X
Vital Signs	X[7]	X[6]	X[7]	X[6]	X[7, 12]	X[12]	X[12]
Weight (pre-dialysis)					X[4]	X[4]	X[4]
Weight (post-dialysis)					X[8]	X[8]	X[8]
Record net ultrafiltration during dialysis					X[9]	X[9]	X[9]
Cardiac MRI							X[10]
Hand grip strength							X [11]
Adverse Events	X						
Concomitant Medications	X						

Laboratory test panels are defined in [Appendix D](#)

Every effort should be made to conduct the weekly study visits on the same day of the week (e.g. on Wednesdays)

ET-1 = Early Termination Visit 1 (see [Section 5.8](#))

[a], [b], [c], [d] Please see [Footnote i](#)

[1] The Study Drug is to be administered during dialysis over approximately 1 hour, starting any time prior to the last 1 hour of dialysis (see [Section 6.1.1](#))

- Study Visits during which Study Drug infusions are required should be planned on the same day of the week so that Study Drug administration can occur on a schedule of every 14 days.

- Whenever possible, keep the timing of the start of study drug relative to the start of dialysis constant (e.g., study drug is always started ~15 minutes after dialysis is started)
- Patients who miss a dose of Study Drug (e.g., due to a missed dialysis visit) may receive the missed Study Drug up to 96 hours (or 4 days) later. If the missed dose cannot be administered within this time frame, the dose should be considered “missed” and the next dose administered at the next study visit as planned.

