[2] Serum pregnancy in women of childbearing potential only.

[3] Patients receiving warfarin only. May also be done using a point of care device.

[4] Obtain weight within 30 minutes prior to the start of dialysis. On Weeks 11 and 12, should be recorded for the same dialysis session during which Lab Panel 8 [CARD] data were collected.

[5] Limited physical exam to include skin, oropharynx, lungs, heart, abdomen, extremities (including feet), and any areas suggested by symptoms, with particular attention to signs of infection. May be performed by a physician-investigator or mid-level provider. Record abnormal findings in the source documents.

[6] Obtain blood pressure, heart rate, respiratory rate, and temperature: within 15 minutes prior to starting dialysis.

[7] On Day 1: Obtain blood pressure, heart rate, respiratory rate, and temperature: within 15 minutes prior to starting the infusion; 15±10 and 45±10 minutes following the start of the infusion and 0-15 minutes, 30-45 minutes, and 60-75 minutes following the end of the infusion.

After Day 1: Obtain blood pressure, heart rate, respiratory rate, and temperature: within 15 minutes prior to starting the infusion, 15 ± 10 and 45 ± 10 minutes following the start of the infusion; 0-15 minutes and 30-45 minutes following the end of the infusion.

[8] Within 30 minutes after the end of dialysis. Should be recorded for the **same** dialysis session during which Lab Panel 8 [CARD] was collected.

[9] Net ultrafiltration volume should be recorded for the **same** dialysis session during which Lab Panel 8 [CARD] data were collected.

[10] Obtain during Week 12 (+ 2 weeks).

[11] Perform handgrip strength any time prior to starting dialysis.

[12] Obtain blood pressure, heart rate, respiratory rate, and temperature: within 30 minutes prior to starting dialysis and within 30 minutes after dialysis.

[13] Have patient complete the FACIT-F questionnaire (see instructions in Study Reference Manual) prior to dialysis or during the first hour of dialysis. On Day 1, must be completed before the start of the Study Drug infusion.

[14] Visit window may be extended to +4 days only in instances when the study drug was missed on the targeted visit day and also could not be given during the dialysis visit after the missed dose.

[15] Randomization may be performed on Day -1, if needed. Administration of the first dose of Study Drug will continue to define Study Day 1.

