Appendix D Laboratory Measurements

Laboratory	Panel Name	Tests Included
Central	Panel 1: Chemistry [CHEM]	Sodium, potassium, chloride, bicarbonate (or CO ₂), calcium, phosphate, alanine aminotransferase (ALT), aspartate aminotransferase (AST), blood urea nitrogen (BUN) creatinine, total bilirubin, direct bilirubin, alkaline phosphatase, albumin, glucose
Central	Panel 2: Lipids [LIP]	Total cholesterol, low density lipoprotein (LDL) cholesterol, high density lipoprotein (HDL), triglycerides
Central	Panel 3: Inflammation 1 [INFL1]	serum amyloid A, hepcidin
Central	Panel 4: Special RBC Indices [SPRBC]	reticulocyte hemoglobin concentration (CHr), % hypochromic red cells (%HRC)
Central	Panel 5: Hematology [HEME]	Hemoglobin, hematocrit, reticulocyte count, red blood count (RBC) indices (e.g., mean corpuscular volume (MCV), red cell distribution width (RDW), platelets, white blood count (WBC), WBC differential
Central	Panel 6: Iron Indices [IRON]	TSAT, ferritin, iron, total iron binding capacity (TIBC)
Central	Panel 7: PK [PK]	COR-001
Central	Panel 8: Cardiac Markers [CARD]	Troponin T, NT-proBNP
Central	Panel 9: Infection Screen [INFEC]	HIV 1 and 2, Hepatitis B surface antigen, Hepatitis B surface antibody, Hepatitis C antibody, mycobacterium tuberculosis blood test (i.e., interferon gamma release assay)
Central	Panel 10: Anti-Drug Antibodies [ADA]	Anti-COR-001 binding antibodies and neutralizing antibodies (if binding antibodies are detected)
Central	Panel 11: Inflammation 2 [INFL2]	Total and free IL-6
Central	Panel 12: Future biomarkers [BIO]	Future cardiac, renal, and hematologic markers, including gene variations, ribonucleic acid, or protein markers
Central	Panel 13: B-Vitamins [BVIT]	B-12, folate
Central	Other individual tests	Screening (total) IL-6, genotype, intact parathyroid hormone [PTH], lipoprotein a [Lp(a)], pregnancy [β -hCG in women of childbearing potential only], follicle-stimulating hormone (FSH), stool occult blood, pre-albumin, hsCRP
Local	Coagulation	International normalized ratio (INR) (warfarin-treated patients only)

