2.3 TIME WINDOWS FOR ANALYSIS

If data are collected by visit, the data will be analyzed by visit based on the protocol-planned visits. If multiple records are collected for a visit, the latest record will be used for the summary for that visit. Unless otherwise specified, baseline is defined as the last non-missing value prior to initiation of study drug. Early termination visit will be mapped to the post-baseline scheduled visit. After mapping, if there is more than one visit in the same window, the scheduled visit will be used if available. If there is no scheduled visit in the same window, the mapped visit closer to the target assessment day will be used. If more than one visit has the equal distance to the target day, then the later one will be used. The unscheduled visit will not be included in the by-visit summary, but will be included in the outlier analysis.

The observational period for the study will start from informed consent and end with study completion (see [Section 3.1](#) for the definition of study completion). Any event occurring after the defined observational period, even if collected on the CRF, may not be included in the summary statistical analysis. However, all data, including that reported after the defined observational period, will be included in the patient data listings.

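### The SAP's Weeks 10–11 window for troponin and NT-proBNP does not match the schedule, which draws them on treatment only in Weeks 11 and 12; protocol 11.4.4 has the window that fits

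*SAP*

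**What the plan says.** Both documents list the change in pre-dialysis, post-dialysis and delta troponin and NT-proBNP among the exploratory pharmacodynamic endpoints, but they give two different windows.

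- SAP 1.2.3.2 (exploratory list), SAP 7.3 and protocol 3.1.3: "from baseline (mean of Screening) to Weeks 10 – 11".
- Protocol 11.4.4: "from baseline (mean of Screening) to Weeks 11 – 12".

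The two markers make up Panel 8 in protocol Appendix D. In the Appendix A Schedule of Events, the Treatment Period entries for that panel are Day 71, Day 75 and Day 78, each before and after dialysis. The column headings place the first two in Week 11 and the third in Week 12/ET-1. Appendix A footnote 4, on pre-dialysis weight, uses the same weeks: "On Weeks 11 and 12, should be recorded for the same dialysis session during which Lab Panel 8 [CARD] data were collected".

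Two rules in SAP 2.3 decide which week a value belongs to. The general rule is that "the data will be analyzed by visit based on the protocol-planned visits". For patients who leave early, "Early termination visit will be mapped to the post-baseline scheduled visit".

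**The concern.** A programmer working from SAP 7.3 would look for cardiac values at Weeks 10 and 11. Nothing is scheduled at Week 10, and the Week 12 session lies outside the window. That session is collected like the other two, with paired blood samples, pre- and post-dialysis weights and net ultrafiltration (protocol 5.4.12 to 5.4.14).

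Early termination adds to the problem. Under protocol 5.8, a patient who leaves before Week 12 has the Week 12 procedures at ET-1. For a patient who leaves before Day 71, that is the only scheduled post-baseline cardiac draw. If it is labelled Week 12, a Weeks 10–11 window excludes that patient from the endpoint.

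The markers appear in a secondary objective (protocol 2, SAP 1.1.2) and in the interim list (SAP 10.2), so the window should be settled before any output is produced.

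**Working it through.** The plan gives no numerical figure to reproduce here. The check compares each window with the schedule.

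**Step 1. Place the visits in weeks.** Nominal week = day ÷ 7, rounded up. This agrees with the Appendix A column headings.

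| Study day | Day ÷ 7 | Nominal week | Cardiac panel scheduled | Completed weeks, (day − 1) ÷ 7 |
|---|---|---|---|---|
| 64 | 9.14 | 10 | No | 9.0 |
| 71 | 10.14 | 11 | Pre and post | 10.0 |
| 75 | 10.71 | 11 | Pre and post | 10.6 |
| 78 | 11.14 | 12 (ET-1) | Pre and post | 11.0 |

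Appendix A has no cardiac panel at any other Treatment Period visit and none in follow-up.

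**Step 2. Apply the two windows by planned visit.**

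- Weeks 10–11: Days 71 and 75. This is 2 of 3 sessions, or 4 of 6 samples. Week 10 contributes none.
- Weeks 11–12: Days 71, 75 and 78. This is 3 of 3 sessions, or 6 of 6 samples, and no week is empty.

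**Step 3. Size of the loss if visits are averaged.** The plan does not say that they are, so this is only an illustration. Assume each visit has the same variance s² and any two visits have correlation ρ. The variance of a mean of m visits is

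s² × [1 + (m − 1)ρ] ÷ m.

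The ratio of two visits to three is [(1 + ρ) ÷ 2] ÷ [(1 + 2ρ) ÷ 3].

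| Assumed ρ | Two visits (× s²) | Three visits (× s²) | Ratio | Increase |
|---|---|---|---|---|
| 0 | 0.500 | 0.333 | 1.500 | 50% |
| 0.5 | 0.750 | 0.667 | 1.125 | 12.5% |
| 0.8 | 0.900 | 0.867 | 1.038 | 3.8% |
| 0.9 | 0.950 | 0.933 | 1.018 | 1.8% |

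The documents give no value of ρ. Zero is the extreme case. The three draws come from one patient within eight days (Days 71 to 78), so a positive correlation is the more natural assumption.

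**The case against.** **The window could be counted in completed weeks.** On that count the three draws fall at 10.0, 10.6 and 11.0 weeks, and Weeks 10–11 would cover them all. The SAP does count this way once: SAP 7.1 takes the Day 29 value for hsCRP at Week 4. But it states that convention for hsCRP only. SAP 2.3 works by planned visit, and the schedule and footnote 4 label these draws Weeks 11 and 12. The objection does not rescue the text. It does show that loss of Day 78 is not certain, which is a further reason to name the study days.

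**The Day 78 data may still be reported.** SAP 2.1 says that all collected data are summarised unless otherwise specified, so Week 12 values could appear in other summaries. That stands. The point is that the endpoint as defined omits them, not that they are lost. The SAP 10.2 interim list names the markers without weeks and refers back to the SAP's summary approach, so the documents do not settle whether the mismatch carries over.

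**An off-schedule draw could fall in calendar Week 10.** A Day 71 visit held two days early (Day 69) would do so, but by planned visit it is still Week 11.

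**The endpoint is minor.** This stands. It is classed as exploratory and summarised descriptively, and no sample size, power, significance test or safety decision depends on it.

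**Conclusion.** The mismatch is real. One endpoint has two windows, and by planned visit only the Weeks 11–12 window in protocol 11.4.4 fits the samples scheduled. The SAP's window includes one week without a cardiac draw and leaves out one of three sessions. The correction is worth making, but the impact is low.

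A reader might infer more than the documents support:

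- *A 50% loss of precision.* This requires averaging, which the plan does not specify, and uncorrelated visits. With positive correlation the figure falls to between 12.5% and about 2% over the assumed range of 0.5 to 0.9. If visits are summarised separately, it does not apply.
- *Loss of a draw matched to the baseline weekday.* Same-weekday visits are a best-effort request, and Days 71 and 78 carry ±2-day windows. Protocol 5.3 gives Wednesday as an example draw day but asks for Day 1 on a Monday, Tuesday, Thursday or Friday. A weekday match with Screening cannot be derived.
- *Day 71 is compromised as an infusion day.* Its pre-dialysis sample comes before an infusion normally given during dialysis, and the correction keeps Day 71 in any case.
- *Bias through fluid load.* The protocol asks for weight and ultrafiltration from the same session, but neither document says that the markers depend on fluid status.

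None of these is needed for the conclusion, and none should be relied on.

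**What to change.** In SAP 1.2.3.2, SAP 7.3 and protocol 3.1.3, replace Weeks 10–11 with *Weeks 11–12 (Days 71, 75 and 78)*. This agrees with the weeks in protocol 11.4.4, which itself names no study days and no averaging.

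State separately whether the visits are averaged or summarised one by one, for each of the pre-dialysis, post-dialysis and delta values. This is a new decision, not one the protocol already contains. The same sentence should say to which visit an ET-1 cardiac draw is assigned.

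The cost is a change of wording. All the samples are already in the schedule, and no sample size or other analysis is affected.
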